4.12.2 Open-Label Safety Analysis

For the Interim Analysis as well as the Final Analysis, all safety data collected for the Safety Population during the open-label period of the study will be presented using descriptive statistics, including summary tables of AEs, summary tables and graphical plots of mean values over time for continuous measurements (e.g., vital signs, weight), and frequency tables for categorical data obtained at each study visit. Statistical methods and counting rules similar to those described for the double-blind treatment period will be applied. The last measurement obtained prior to the first dose of open-label fosmetpantotenate will serve as the baseline value for assessing change from baseline in clinical laboratory data and vital signs during the open-label period of the study.

4.13 Pharmacokinetic Analysis

Multiple-dose blood concentrations of fosmetpantotenate will be tabulated and summarized using descriptive statistics. For each analyte, concentration by patient, by nominal sample time, and by study day will be tabulated; summary statistics (n, arithmetic mean, geometric mean, coefficient of variation [CV, as percent], minimum, median, maximum) will be provided by nominal sample time and study day.

Additionally, summary statistics by nominal sample time irrespective of study day will also be provided. Graphical presentations of drug concentration will include individual concentration versus time from dose, by study day and irrespective of study day, and mean concentration versus time from dose, by study day and irrespective of study day. Each graph will be provided on linear and log-linear axes.

Fosmetpantotenate concentrations may also be analyzed by nonlinear mixed-effects modeling, either alone or in conjunction with data from other studies. Available metabolite concentrations may be analyzed similarly.

4.14 Biomarkers

Biomarker assessments (succinate, lactate, maleate, pyruvate, alanine, acetone, acetoacetic acid, 3-hydroxybutyric acid, 2-hydroxybutyric acid, and acetylCoA) will be listed and summarized by treatment group and time point using descriptive statistics (mean, median, standard deviation, standard error of the mean, coefficient of variation, minimum, and maximum) and graphical displays. Change from baseline values will be evaluated at each time point, using paired t-tests (within-group) and 2-sample t tests to evaluate differences between treatment groups. Additional exploratory analyses of biomarkers will be described in a separate SAP.

5 References

1. International Conference on Harmonisation of Technical Requirements for Registration of Pharmaceuticals for Human Use, ICH Harmonised Tripartite Guideline, Statistical Principles for Clinical Trials (E9), 5 February 1998.
2. International Conference on Harmonisation of Technical Requirements for Registration of Pharmaceuticals for Human Use, ICH Harmonised Tripartite Guideline, Structure and Content of Clinical Study Reports (E3), 30 November 1995.
3. Prakash A., et. al. The impact of analytic method on interpretation of outcomes in longitudinal clinical trials. International J. of Clinical Practice. 2008; 62, 8: 1147-1158.
5. Rubin, D.B. (1987) Multiple Imputation for Nonresponse in Surveys. John Wiley & Sons Inc., New York.

6. Mantel, N. and Haenszel, W. Statistical Aspects of Analysis of Data from Retrospective Studies of Disease. *Journal of the National Cancer Institute*. 1959; 22, 719–748.
7. The EuroQol Group. EuroQol-a new facility for the measurement of health-related quality of life. *Health Policy* 1990; 16(3):199-208.

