DOSE/ROUTE/REGIMEN (TEST ARTICLE):

Fosmetpantotenate will be supplied in dried powder form for reconstitution and oral administration, packaged in a dose strength of 75 mg capsules, and, after receipt of regulatory approval, 75 mg and 300 mg sachets. In all patients, the 24-week double-blind period will begin with dose escalation on Days 1 through 3 (described below), followed by the full dose starting on Day 4. The full dose for patients aged 18 to 65 years will be 300 mg TID for a total daily dose of 900 mg. The full dose for patients aged 6 to <18 years will be determined by weight at screening: patients weighing ≥ 40 kg will receive 300 mg TID for a total daily dose of 900 mg (ie, the same as patients aged 18 to 65 years); patients weighing ≥ 20 kg but <40 kg will receive 150 mg TID for a total daily dose of 450 mg; and patients weighing <20 kg will receive 75 mg TID, for a total daily dose of 225 mg. All doses of investigational product will be taken with food.

Dose escalation on Days 1 through 3 will proceed as follows, based on age and weight at screening:

Patients aged 18 to 65 years and patients aged 6 to <18 years weighing ≥ 40 kg: On Day 1, patients will receive one 300 mg dose (in the morning); on Days 2 and 3, they will receive 300 mg twice daily (BID, at least 8 hours apart) for a total daily dose of 600 mg; and on Day 4, they will receive the full dosage of 300 mg TID (given at approximately 8 hour intervals) for a total daily dose of 900 mg.

Patients aged 6 to <18 years weighing ≥ 20 kg but <40 kg: On Day 1, patients will receive one 150 mg dose (in the morning); on Days 2 and 3, they will receive 150 mg BID (at least 8 hours apart) for a total daily dose of 300 mg; and on Day 4, they will receive the full dosage of 150 mg TID (given at approximately 8 hour intervals) for a total daily dose of 450 mg.

NAME OF COMPANY

Retrophin, Inc.
[name]
USA

NAME OF FINISHED PRODUCT

fosmetpantotenate (RE-024)

NAME OF ACTIVE INGREDIENT

Methyl 3-((2R)-2-hydroxy-4-((((S)-1-methoxy-1-oxopropan-2-yl)amino)
(phenoxy)phosphoryl)oxy)-3,3-dimethylbutanamido propanoate

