9.4. Pharmacokinetic Assessments

Whole blood samples for PK analyses will be obtained at visits specified in the schedule of assessments in [Section 15.1](#). All patients will have a pre-dose blood draw at Baseline. For subsequent visits at which PK samples are obtained following the first dose of the day, patients will undergo 2 blood draws according to randomization to one of the sampling schemes in Table 2. Within each treatment group (ie, fosmetpantotenate and placebo), the number of patients assigned to each sampling scheme will be approximately equal, and the assignment will remain the same for all visits at which PK samples are obtained. The actual time of in-clinic administration of investigational product, and the exact time of each blood draw for PK analysis will be recorded to the nearest minute on the eCRF.

Table 2: Pharmacokinetic Sampling Schemes

Scheme Number	Blood Draw 1 (Minutes Post Dose)	Blood Draw 2 (Minutes Post Dose)
1	10 ± 5	60 ± 10
2	10 ± 5	210 ± 15
3	10 ± 5	420 ± 15
4	20 ± 5	60 ± 10
5	20 ± 5	210 ± 15
6	20 ± 5	420 ± 15
7	45 ± 5	60 ± 10
8	45 ± 5	210 ± 15
9	45 ± 5	420 ± 15

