- ¹⁵ To be conducted in patients 12 years of age and older. The Investigator should use clinical judgment to determine whether or not a patient with a positive test result should be admitted to the study (eg, if the Investigator believes that the result may be indicative of a drug or alcohol disorder, that the patient may not be able to comply with the protocol, or that participating in the study may put the patient at undue risk, the patient should be excluded per the exclusion criteria).
- ¹⁶ To be administered to patients who can safely walk independently or with assistance. Screening evaluation will determine whether the patient can be evaluated during the study.
- ¹⁷ See [Section 9.5.4](#) and [Section 9.5.5](#) for age-based administration guidelines.
- ¹⁸ Diadochokinetic assessments will include alternating motion rate and sequential motion rate. Sites will video record the assessments, which will be rated by a central rater.
- ¹⁹ All patients will have a pre-dose blood draw at Baseline. For subsequent visits, patients will be randomly assigned to a sampling scheme according to [Table 2](#); assignment will remain the same for all visits. The actual time of administration of investigational product, and the exact time of blood sampling for PK analysis will be recorded to the nearest minute on the eCRF.
- ²⁰ At Baseline, 3 samples will be collected for biomarkers; the first will be collected prior to any assessments, and all 3 will be collected at least 3 hours apart.

- ²¹ At the Week 1 Day 4, Week 6, and Week 18 visits, 2 samples will be collected for biomarkers, at the times of PK sample collection.
- ²² At the Week 24 visit, 2 samples will be collected for biomarkers at least 3 hours apart. If the patient prematurely discontinues study medication, but does not withdraw from the study, 2 samples should be collected at least 3 hours apart at the End of Treatment visit.
- ²³ In order to provide training in proper administration, investigational product will be prepared and administered by site personnel, together with the patient and/or family/caregiver, during in-clinic patient visits. Following adequate training, doses may be self-administered by the patient or caregiver at the site's discretion.
- ²⁴ Blinded investigational product dispensation is not performed at the Week 24, End of Treatment Early Termination visits.

Table 15.1-2 Open-Label Period

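### At Day 4, Week 6 and Week 18 the within-group paired t-tests on biomarkers cannot separate a drug response from the change in sampling conditions since Baseline

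*SAP*

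**What the plan says.** **Analysis.** SAP 4.14 says "Change from baseline values will be evaluated at each time point, using paired t-tests (within-group", and in the same sentence plans "2-sample t tests to evaluate differences between treatment groups". Protocol 12.10 plans only descriptive statistics and plots for biomarkers, so both sets of t-tests come from the SAP.

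**Sampling** (footnotes to Protocol Table 15.1-1):

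- Baseline, Day -1, three samples: "the first will be collected prior to any assessments, and all 3 will be collected at least 3 hours apart".
- Post-dose visits: "Week 1 Day 4, Week 6, and Week 18 visits, 2 samples will be collected for biomarkers, at the times of PK sample collection".
- Week 24: "At the Week 24 visit, 2 samples will be collected for biomarkers at least 3 hours apart".

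**PK times.** Protocol 9.4 ties the draws to the first dose of the day: "For subsequent visits at which PK samples are obtained following the first dose of the day, patients will undergo 2 blood draws". Patients are randomised to one of nine schemes. The first draw is at 10, 20 or 45 minutes and the second at 60, 210 or 420 minutes. Schemes are used about equally within each arm, and a patient keeps the same scheme at every visit. The synopsis adds: "All doses of investigational product will be taken with food".

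**Recording.** Protocol 9.6.1 has the in-clinic dosing time and the exact sampling time recorded to the minute. No fasting, meal or clock-time rule is stated for any biomarker sample.

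**The concern.** A paired t-test treats every systematic difference between two occasions as change. Between Baseline and Day 4, Week 6 or Week 18, time since a dose taken with food differs by design. A drug effect and a sampling effect would look the same in the fosmetpantotenate arm's paired result.

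The listed analytes include lactate, pyruvate, alanine and ketone bodies. That they vary with meals or time of day is a premise brought to the documents, not something they state. The confounding is in the design either way; the premise affects only its size.

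At stake is the meaning of a small within-group p-value. Both documents list the biomarkers' possible response to treatment as an objective, so a significant paired test on active drug would naturally be read as a pharmacodynamic response, even where placebo sampling would give the same shift.

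**Working it through.** **1. Sampling conditions side by side**

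| Visit | Samples | Tied to a dose? |
|---|---|---|
| Baseline (Day -1) | 3, at least 3 h apart | No; before any dose |
| Day 4, Weeks 6 and 18 | 2, at PK times | Yes; nominally 10 to 420 min after the first dose of the day |
| Week 24 | 2, at least 3 h apart | Not stated |

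With the nine schemes used equally, 12 of 18 draws (67%) are nominally within 60 minutes of the dose. The gaps between draws are 50, 200, 410, 40, 190, 400, 15, 165 and 375 minutes, so 4 of 9 schemes have draws less than 3 hours apart.

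**2. Group size.** SAP 4.2 gives 37 per arm for a 3-point difference with SD 4.5. The noncentrality is (3/4.5) × √(37/2) = 2.867, and the exact t-test power is 80.8%. The plan's figure reproduces.

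**3. Paired test with no drug effect.** Let the sampling shift be d SDs of the change score (assumed; the documents give no biomarker SD or meal effect). The noncentrality is d√n on n − 1 degrees of freedom, two-sided 5%.

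| d | n = 37: d√n | Rejects (critical 2.028) | n = 12: d√n | Rejects (critical 2.201) |
|---|---|---|---|---|
| 0 | 0 | 5% | 0 | 5% |
| 0.2 | 1.217 | 22% | 0.693 | 10% |
| 0.3 | 1.825 | 43% | 1.039 | 16% |
| 0.5 | 3.041 | 84% | 1.732 | 35% |

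The n = 12 columns apply if a time point means a nominal post-dose time: each of the six times belongs to 3 of 9 schemes, and 37 × 3/9 ≈ 12. SAP 4.14 does not say which meaning applies. If each visit is one time point, the three dose-timed visits carry 10 biomarkers × 3 visits × 2 arms = 60 paired tests.

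**4. Between-arm test with no drug effect** (simulation, 20,000 runs, 37 per arm). With a shift of 0 to 0.8 SD common to both arms, the 2-sample t-test rejects 4.8% to 5.3% of the time. With shifts that vary by scheme and schemes balanced, it rejects 3.0% to 4.5%. It is not inflated. Below 5% it is conservative, because scheme variation enters the error term but not the difference between arms.

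**5. What ignoring scheme costs.** Borrow the PKAN-ADL effect size, 3/4.5 = 0.667 SD, as an illustration.

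- With no scheme effect, power is 81% with or without scheme in the model.
- With scheme means spread by 0.5 SD (assumed), the plain test's error SD is √(1 + 0.25) = 1.118. The difference must then exceed about 1.993 × √(2/37) × 1.118 = 0.518. Its true standard error is √(2/37) = 0.2325, so power ≈ P(Z > (0.518 − 0.667)/0.2325) ≈ 74%; simulation gives 73% to 74%. With scheme in the model, power stays near 80%.

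**6. Which samples form the change.** SAP 4.14 has no rule. The general rules take the last value before first dose (SAP 6.2.2) and the last value at each visit (SAP 4.1). If these cover planned replicates, the change is the third Day -1 sample, at least 6 hours after the first, against the draw at 60, 210 or 420 minutes. The SAP does not say that this is intended.

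**The case against.** The strongest reply is that the SAP already contains the valid comparison. The 2-sample t-tests stand in the same sentence, placebo follows the same schedule, and results are shown by treatment group, so a shift on placebo would be visible beside the active arm. This stands. It confines the defect to the inferential use of the within-group p-values.

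A reader might infer more than the documents support:

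- *That Baseline and Week 24 samples are untimed.* They are not. Minimum spacing is set, the first Baseline sample precedes all assessments, and exact times are recorded. They are only not tied to a dose, meal or clock time.
- *That Week 24 is equally affected.* Its spacing rule is nearly the Baseline rule, so it is less affected. It is not immune, since its samples have no stated relation to a dose or meal.
- *That a false response of known size is expected.* The rejection rates are paired-test power at chosen shifts. With no meal rule at Baseline, even the direction of a shift is unknown.
- *That the between-arm result is biased.* Approximate balance of schemes within arms argues against this, and the simulation agrees.

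Two further replies also stand. Scheme adjustment serves precision, not validity, and nine levels leave about 4 patients per scheme per arm (37/9). The endpoint is exploratory, and SAP 4.14 defers further biomarker analyses to a separate plan, not available here. That plan may refine the modelling, but the paired tests are specified in this one.

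**Conclusion.** The point holds for the paired tests at Day 4, Week 6 and Week 18. Following the plan as written gives within-group p-values that cannot distinguish drug response from a change in sampling conditions. That conclusion rests on the schedule alone. Its size rests on an assumed shift and on the meaning of time point: 22% to 84% false rejection for 0.2 to 0.5 SD at 37 patients, or 10% to 35% at about 12. The between-arm test is sound but gives up some power if biomarkers vary with time since dose. No primary or secondary conclusion is affected. The change is worth making because it is cheap and because these p-values invite a reading that they cannot support.

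**What to change.** In SAP 4.14:

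1. Report within-group changes descriptively, without inferential p-values, as Protocol 12.10 plans.
2. Base any statement of biomarker response on the between-arm difference in change from baseline.
3. At Day 4, Week 6 and Week 18, fit that comparison with the randomised PK scheme as a factor, or with the recorded minutes post dose of each draw as a covariate.
4. State how the three Baseline and two post-baseline samples form the change score, and whether a time point is a visit or a nominal post-dose time.

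Cost: SAP wording only. The IWRS assigns the scheme and the times are already collected. Within-group p-values are lost, and the scheme factor uses up to 8 degrees of freedom (72 to 64 with 74 patients), which cost no visible power in the check with no scheme effect.

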4.1 General Statistical Considerations

Tabulations of summary statistics, graphical presentations, and statistical analyses will be performed using SAS® Version 9.3 or higher. All data collected will be summarized using descriptive statistics, including mean, standard deviation (SD), median, minimum, and maximum for continuous variables, and frequency tables with counts and percentages for categorical variables. Age group categorization will be consistent with the Protocol Version that was applicable at time of patient randomization.

Unless otherwise stated, the “baseline” assessment for the double-blind period will be defined as the last measurement obtained prior to the first dose of blinded investigational product (pre-dose on Day 1). For patients who enter the open-label extension period, the baseline value will be re-defined for the open-label period as the last observation prior to start of open-label fosmetpantotenate, unless otherwise specified.

As appropriate, the scales used as efficacy endpoints to measure neurological impairment, dystonia, motor function, and quality of life will be scored and/or normalized in accordance with user manuals and published scoring procedures for each instrument. For each scale, the prescribed rules for deriving the total score in the presence of 1 or more missing items will be followed.

Unless otherwise noted, if at least 80% of the items for a scale (i.e., PKAN-ADL, UPDRS Part III, BAD, Neuro-QOL) are non-missing, then the prorated total score for the scale is obtained by summing the non-missing item responses, multiplying by the total number of items in the scale, and then dividing by the number of non-missing items.

There are two patients who had a question (item) on the PKAN-ADL mistranslated for screening and baseline visits. In analyses using the Double-Blind Full Analysis Set, the values for this item will be rendered invalid, set to missing, and the PKAN-ADL total score will be prorated as described above. The invalid values will be presented and flagged in the data listing, as originally recorded.

For by-visit summaries, the last non-missing assessment (including repeat assessments, if any) recorded at each visit will be used for summarization. For across visit summaries (e.g. maximum post-baseline value), scheduled, unscheduled (if any) and repeat assessments will all be considered for the value to be analyzed; all observations will be presented in data listings.

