4.10.4 Adjustment for Multiple Hypothesis Testing

To control the Type 1 familywise rate at 5%, the serial gate-keeping approach (proposed by [Westfall and Krishen, 2001](#)) will be used to test the primary and secondary efficacy endpoints (ordered by clinical relevance and importance) during the double-blind period in the above specified sequence. It will be implemented in the following way: If (and only if) the null hypothesis associated with the primary endpoint is rejected at the 0.05 significance level, then the secondary efficacy endpoint will be tested at the 0.05 significance level. The plan for analysis of other endpoints during the double-blind period is purely exploratory, so no further adjustment is warranted. Similarly, efficacy analyses of endpoints collected during the open-label period are also exploratory, and do not warrant adjustment.

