6.2.2 Visits

Relative Study Day: The date of first dose of study treatment is Day 1. A minus (–) sign indicates days prior to date of first dose (e.g., Day -5 represents 5 days before first dose.) There is no Day 0.

If a visit is before the date of first dose, the relative study day is calculated as (Visit Date – Date of First Dose). Otherwise, the relative study day for a specific visit is calculated as (Visit Date – Date of First Dose +1).

- Baseline: For all study variables, baseline for the double-blind period is defined as the last measurement obtained prior to the first dose of double-blind study medication, unless otherwise specified; for the open-label extension study, baseline is the last measurement obtained prior to the first dose of open-label study medication (fosmetpantotenate).
- Post baseline: post baseline visits will be nominal visits, as scheduled in the protocol.

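### Between-arm biomarker tests are unadjusted t-tests on change from what is by default one of three baseline samples; ANCOVA on the mean baseline would be more precise at no cost

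*SAP*

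**What the plan says.** **Test.** SAP Section 4.14 states: "Change from baseline values will be evaluated at each time point, using paired t-tests (within-group) and 2-sample t tests". The between-arm part of that sentence is "2-sample t tests to evaluate differences between treatment groups". It names no covariate, no biomarker-specific baseline and no rule for combining several samples from one visit. Protocol Section 12.10 plans only listings, descriptive statistics and plots for biomarkers, so the tests are an addition in the SAP.

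**Samples.** Protocol Section 15.1, footnotes to Table 15.1-1: "At Baseline, 3 samples will be collected for biomarkers", all at least 3 hours apart and the first before any assessment. At Day 4, Week 6 and Week 18 two samples are taken at the PK sampling times. For the last double-blind visit: "At the Week 24 visit, 2 samples will be collected for biomarkers at least 3 hours apart".

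**Baseline rule.** SAP Section 6.2.2: "For all study variables, baseline for the double-blind period is defined as the last measurement obtained prior to the first dose". That sentence goes on to allow for another specification. SAP Section 4.1 gives the same default.

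**Within-visit rule.** SAP Section 4.1, for by-visit summaries: "the last non-missing assessment (including repeat assessments, if any) recorded at each visit will be used for summarization".

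**Status.** SAP Section 4.10.4: "The plan for analysis of other endpoints during the double-blind period is purely exploratory, so no further adjustment is warranted". Section 4.14 adds: "Additional exploratory analyses of biomarkers will be described in a separate SAP".

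**The concern.** The between-arm biomarker comparison discards precision that the trial has already paid for, in two ways. First, a t-test on change subtracts the whole baseline value, noise included, where ANCOVA subtracts only the part that predicts follow-up. Second, under the default baseline rule the first two Day -1 samples do not enter the test.

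The choice also departs from the SAP's own practice. FIM/WeeFIM and DDK are exploratory too, and the SAP analyses them by ANCOVA with treatment, age group and baseline (Sections 4.10.3.4 and 4.10.3.5). The primary and secondary models adjust for the same two factors, and age group is a randomization stratum.

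Exploring biomarker response to treatment is a stated objective, and about 82 patients are randomized. A noisy comparison could miss a biomarker signal, or leave it too imprecise to interpret. The efficacy claim itself is not at stake.

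**Working it through.** **Figures in the plan.** There is no biomarker SD, correlation, power or sample size to reproduce. The only calculation is for PKAN-ADL (difference 3, SD 4.5, 37 per arm). It holds, with exact t-test power of 80.8% at 37 per arm, but says nothing about biomarkers. I use it only as the simulation size.

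**Assumed inputs (not in the documents).**
- ρ, the correlation of a Day -1 sample with a follow-up sample: 0.3 to 0.8.
- r, the correlation between two Day -1 samples: from ρ up to 0.95.
- Equal variance (set to 1) at baseline and follow-up, one post-baseline value, no age effect.

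**Variance of the treatment difference, up to a common factor.**
- t-test on change from the last baseline: 2(1 − ρ)
- t-test on change from the mean of three: 1 + (1 + 2r)/3 − 2ρ
- ANCOVA on the last baseline: 1 − ρ²
- ANCOVA on the mean of three: 1 − 3ρ²/(1 + 2r)

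The first minus the third is 2(1 − ρ) − (1 − ρ²) = (1 − ρ)². So in large samples ANCOVA on even a single baseline beats the planned test for every ρ below 1.

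**Worked corners.**
- ρ = r = 0.3: planned 2 × 0.7 = 1.400. ANCOVA, single: 1 − 0.09 = 0.910, a cut of 35.0%. ANCOVA, mean of three: 1 − 0.27/1.6 = 0.831, a cut of 40.6%.
- ρ = 0.8, r = 0.95: planned 2 × 0.2 = 0.400. ANCOVA, single: 1 − 0.64 = 0.360, a cut of 10.0%. ANCOVA, mean of three: 1 − 1.92/2.9 = 0.338, a cut of 15.5%.

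**Variance reduction against the planned t-test.**

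| ρ | r | Average baselines, keep t-test | ANCOVA, last baseline | ANCOVA, mean of three |
|---|---|---|---|---|
| 0.3 | 0.3 | 33.3% | 35.0% | 40.6% |
| 0.3 | 0.9 | 4.8% | 35.0% | 35.5% |
| 0.5 | 0.5 | 33.3% | 25.0% | 37.5% |
| 0.5 | 0.8 | 13.3% | 25.0% | 28.8% |
| 0.5 | 0.9 | 6.7% | 25.0% | 26.8% |
| 0.7 | 0.7 | 33.3% | 15.0% | 35.4% |
| 0.7 | 0.9 | 11.1% | 15.0% | 20.8% |
| 0.8 | 0.8 | 33.3% | 10.0% | 34.6% |
| 0.8 | 0.95 | 8.3% | 10.0% | 15.5% |

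For standard errors, √(1 − 0.155) = 0.92 and √(1 − 0.406) = 0.77, so they are about 8% to 23% smaller.

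**Simulation** (37 per arm, 6000 runs), ANCOVA on the mean of three: 40.8% against 40.6% by formula (ρ = r = 0.3); 34.8% against 37.5% (0.5, 0.5); 29.0% against 28.8% (0.5, 0.8); 21.1% against 20.8% (0.7, 0.9). Agreement is within about 3 points.

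**Can the post-baseline samples be averaged too?** Protocol Section 9.4 randomizes patients to nine PK schemes: draw 1 at 10, 20 or 45 minutes after the dose, draw 2 at 60, 210 or 420 minutes. Biomarker samples at Day 4, Week 6 and Week 18 follow those times. A visit mean would combine 10 and 420 minutes in one patient and 45 and 60 in another. Week 24 samples are not tied to the schemes, so they can be averaged. Any gain from that is outside the table.

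**The case against.** Much can be said for leaving the section alone. The tests are exploratory and a t-test on change is unbiased under randomization. A separate biomarker SAP, not among the documents, may define baseline differently. Using only the last sample is an inference from a general default. All of this stands, and it limits how far the point can go. The separate SAP is, however, described as covering additional analyses; nothing says that it replaces the tests written here.

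Four stronger readings are tempting and are not supported.

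- **Two-thirds of the baseline blood is wasted.** Section 4.14 lists and summarizes the assessments by time point. The earlier draws are left out of the change-from-baseline test only.
- **The loss is a quarter to two-fifths.** No document gives a correlation from which to derive this. It is one part of the range above, and the reduction falls to 15.5% at ρ = 0.8, r = 0.95.
- **The loss comes from ignoring two samples.** When same-day samples agree closely, most of the gain comes from ANCOVA. At ρ = 0.5 and r = 0.8 the single-baseline ANCOVA already gives 25.0 of the 28.8 percentage points. Averaging matters more when r is close to ρ.
- **The SAP also drops the first post-baseline sample from the test.** The last-value rule in Section 4.1 governs by-visit summaries, whereas Section 4.14 tests at each time point. The two draws may be meant as separate time points. The text does not settle it.

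**Conclusion.** The concern holds as a missed, cost-free gain in precision and a gap in specification. It does not show bias or an error in any confirmatory analysis. As written, the between-arm biomarker test is unadjusted and, by default, uses one of three Day -1 samples as baseline. Under assumed ρ of 0.3 to 0.8 and r from ρ to 0.95, ANCOVA on a single baseline cuts variance by about 10-35%, and on the mean of three by about 15-41%. These figures rest on equal variances, a single post-baseline value and large-sample formulas, and the true correlations are unknown. The direction does not depend on the values chosen within that range. Primary and secondary tests, sample size and error control are unaffected.

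**What to change.** In SAP Section 4.14:

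1. Define the biomarker baseline as the mean of the available Day -1 samples (three planned), and use that same value in the within-group paired tests.
2. Replace the between-group t-test with ANCOVA on treatment and age group, with that mean as covariate. This is the model already set out for FIM/WeeFIM and DDK.
3. At Week 24, use the mean of the two samples as the outcome.
4. At Day 4, Week 6 and Week 18, do not average across PK scheme times. Analyse draw 1 and draw 2 separately, with nominal post-dose time in the model.
5. State that the separate biomarker SAP adds to these definitions, or cross-refer to it if it defines them.

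The cost is SAP wording and minor programming before unblinding. No extra samples, visits or patients are needed.
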